The aim of the present project is to demonstrate the impact of the modulation of executive functions, particularly subserved by DLPFC, on language production in healthy bilingual. We propose that such impact will be particularly present in non-native languages (L2).

The project will tackle the question of the role of prefrontal system and executive functioning (namely updating/working memory system, subserved by the left DLPFC) in language performance in the L1 and in L2. The core question will be whether stimulation of DLPFC will influence lexical access and language production.

The experimental task will test the impact of prefrontal stimulation by rTMS (excitatory, inhibitory, sham) applied to the DLPFC of healthy adult bilingual subjects during two tasks relying on lexical strategies: a picture naming task in L1 and L2 and a word translation task. The EEG correlates of the two tasks performed in the first and second language following rTMS will be analyzed. The EEG study will allow us to investigate precisely the spatiotemporal brain dynamics underlying the behavioral modifications induced by the modulation of left frontal areas.

The hypothesis is that:

1. Excitatory rTMS applied to the left DLPFC will increase performance and/or decrease response time in naming, particularly in L2 naming and in the translation task versus sham and inhibitory rTMS.
2. Excitatory rTMS is expected to modify the cortical activity related to the language tasks. During naming, EEG analyses will show a main effect of stimulation and an interaction between the factors Language (L1 or L2) and Stimulation (excitatory rTMS versus sham and inhibitory rTMS versus sham) at the topographic level, showing an effect of prefrontal areas larger in L2 than L1. The latency of the ERP modulation by rTMS in L2 will allow us to target the dynamics and the language planning processes) underlying improved naming performance.

Methods:

The experimental task will include 80 healthy L1-L2 unbalanced control subjects. We will analyze the influence of the DLPFC activation and inhibition on naming and complex language production task (i.e. translation ability) using rTMS as well as their EEG correlates in L1 and in their best second language (L2). The prediction is that left prefrontal stimulation will increase language performances particularly in L2. EEG analyses will unravel the spatio-temporal dynamics of executive processes involved in the two tasks.

EEG

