To assess language immersion, participants will be asked for the age of acquisition, how long they lived in a region where predominantly German and English language was spoken, the language spoken with family members, when they were child, in their current daily life, and if the language was acquired in or out of school. With regards to the self-evaluation part, participants will indicate in an analogue scale from 1 to 100% how they estimate their reading, speaking, comprehension and writing skills. As a third level of assessment, a sub-test from the computer-based DIALANG language diagnosis system (Zhang and Thompson, 2004 [14]) will be used to evaluate reading performance (see Buetler et al 2014 for a similar procedure [15]).

Procedure

Participants will be randomized to take part in either an inhibitory or excitatory rTMS session. In all sessions, the same evaluations/tasks will be used. Each session starts with sham rTMS-controlled baseline tasks.

At the beginning of the session, the individual motor threshold for the subject's relaxed small hand muscles will be determined by stimulating the right motor cortex with single pulses (e.g. Nyffeler et al., 2008 [16]). This will last about 5-10 minutes. For the rTMS session, we will be using a "theta-burst" rTMS protocol (Nyffeler et al., 2008 [16]; Huang et al., 2005 [17]), in which one of the co-applicants has extensive experience. This stimulation takes 30 seconds to 5 minutes and the resulting effects have been shown to last about 30 minutes. Each rTMS session will be conducted following suggested international rTMS guidelines (Wassermann et al., 1998 [18]).

After applying rTMS, two language tasks will be performed by the participants while an EEG will be recorded. The two language contexts (German and English) will be presented within each of the two sessions in a randomized order. EEG electrodes will be applied before the stimulation. Participants will be seated in an electrically shielded and sound attenuated booth in front of a LCD screen. Stimulus delivery and response recording are controlled using E-Prime 2.0 (Psychology Tools, Inc., Pittsburgh, PA). The stimuli will be presented in the center of the screen. Both behavioral and EEG data will be recorded.

Stimuli and tasks

This study will be conducted in parallel to the previously accepted study A. For this second addendum, there will be no translation task and a different non-verbal task.

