With the specific stimulation parameters used in our protocol, 30 minutes after applying rTMS (inhibitory/excitatory), it can be assumed that the after-effect of the stimulation will have disappeared. Participants will then perform a verbal fluency task (the subject will be asked to name as many words as he/she can which starts with a certain letter during 1 minute). Furthermore, a non-verbal fluency task (5 points test, i.e. a sheet of paper with 40 squares of fixed symmetrically arranged points (5 points) will be presented to the participant. The participant will be asked to produce as many different figures as possible with connecting the dots with at least one line connecting two dots during 2 minutes). Finally, participants will perform a 1-minute verbal fluency task in L2.

Behavioral and EEG analyses

Behavioral analysis

A first behavioral analysis will compare naming and translation performances, as well as speech onset latencies in both languages.

For statistical analyses we will compute two 2 way-ANOVAs for repeated measures with the within-subject factors *Language* (L1 vs L2) and *Stimulation* (inhibitory vs sham or excitatory vs sham). Moreover, we will compute two mixed-model ANOVAs with *Language* (L1 vs L2) as within-subject factor and *Hemisphere* (left vs. right) or *Stimulation* (inhibitory vs excitatory) as between-subject factors.

Event Related Potentials analyses

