The analyses will be conducted with the same principles as in our prior works with reading and naming tasks. ERPs will be analyzed using a step-wise procedure that permits the time-wise, multifactorial statistical assessment of (1) the dynamic changes of scalp-recorded electric field configuration and their temporal segmentation into quasi-stable functional micro-states indexing modulations of the configuration of intracranial generators, (2) global electric field power indexing modulation of response strength of the intracranial generators, (3) intracranial distributed linear electrical source estimations (e.g. Brunet et al., 2011 [21]; Murray et al., 2008 [22]). These analyses will be conducted for each time frame of the whole ERP time-period; however, specific time windows are planned to be sensitive to our factors according to meta-analyses [19] and our previous results: lexical selection is thought to occur between 170 and 270 ms after picture presentation, so there will be a first time window until 200 ms, a second time window between 200 and 300 ms, and a later time window (300-450 ms) corresponding to lexical-phonological encoding in previous studies. The main effect will be L1 and L2 patterns in term of amplitude, duration and sequences. Then, a second main effect will be the left inhibitory/excitatory/sham effect in an early time window before the vocalization will start. We will expect an interaction between language and stimulation, due to the fact that left DLPFC excitatory rTMS will modulate L2 more than L1.

References

1. Green, D.W., et al., Language control and parallel recovery of language in individuals with aphasia. *Aphasiology*, 2010. 24(2): p. 188-209.
2. Abutalebi, J., et al., Bilingual aphasia and language control: a follow-up fMRI and intrinsic connectivity study. *Brain Lang*, 2009. 109(2-3): p. 141-56.
3. Machii K. et al. 2006. Safety of rTMS to non-motor cortical areas in healthy participants and patients. *Clinical Neurophysiology*, 117, 455-471.
4. Lefaucheur JP et al., 2014. Evidence-based guidelines on the therapeutic use of repetitive transcranial magnetic stimulation (rTMS). *Clinical Neurophysiology*, 125, 2150-2206.
5. Osaka N et al., 2007 Transcranial magnetic stimulation (TMS) applied to the left dorsolateral prefrontal cortex disrupts verbal working memory performance in humans. *Neuroscience Letters*, 418, 232-235.

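### The ERP plan treats inhibitory, excitatory and sham stimulation as one main effect, but each participant has sham (always first) plus only one active type; an Arm x Run x Language model is needed

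*Combined protocol and SAP*

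**What the plan says.** All references are to Study A of the combined protocol and SAP.

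- **Event Related Potentials analyses.** After a Language effect, the plan says that "a second main effect will be the left inhibitory/excitatory/sham effect in an early time window", and then expects an interaction between language and stimulation. It gives no ANOVA layout, error term or model.
- **Procedure, allocation.** "Participants will be randomized to take part in either an inhibitory or excitatory rTMS session". The ratio is not stated.
- **Procedure, sham.** "Each session starts with sham rTMS-controlled baseline tasks". Everyone therefore has sham, and has it before the active stimulation.
- **Procedure, sessions.** The two language contexts "will be presented within each of the two sessions in a randomized order", which does not match allocation to a single type of session.
- **Aim, hypothesis 2.** The EEG factor is described as "Stimulation (excitatory rTMS versus sham and inhibitory rTMS versus sham) at the topographic level", that is, as two separate contrasts with sham.
- **Behavioral analysis.** Two repeated-measures ANOVAs use Stimulation as "inhibitory vs sham or excitatory vs sham". Separate mixed ANOVAs cross Language with Hemisphere or with Stimulation, the latter as "inhibitory vs excitatory) as between-subject factors".
- **Methods.** "The experimental task will include 80 healthy L1-L2 unbalanced control subjects". No sample-size calculation is given.

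**The concern.** The three conditions are only partly crossed with participants. Each person supplies sham and one active type, so a factor with all three levels is neither within-subject nor between-subject. The behavioural section separates the two kinds of contrast; the ERP section puts them under one name and does not say how the effect will be tested.

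Two things are at stake. First, an analyst following the ERP section has to choose the model, and the two textbook layouts either cannot be run or are miscalibrated. Second, sham always precedes active stimulation, so practice, fatigue, stimulus repetition or electrode drift can produce a sham-versus-active difference without any stimulation effect. The comparison that randomisation protects is the active-minus-sham change in one arm against the same change in the other. No model in the plan makes it: the behavioural mixed ANOVA that sets inhibitory against excitatory has no sham-versus-active factor.

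**Working it through.** The plan gives no alpha, power, effect size or SD, so it has no figure to reproduce. The check is of structure, supported by simulation.

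**Inputs.** From the documents: 80 participants, and sham first plus one active type each. Assumed: 40 per arm, two-sided 0.05, unit SD for each record, and correlation ρ between a participant's sham and active records of 0.3 to 0.9.

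**1. Three-level repeated-measures ANOVA.** Participants with all three levels: 0 of 80. It cannot be run.

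**2. Three-level between-subject ANOVA on all 160 records** (80 sham, 40 excitatory, 40 inhibitory). This ignores that each person appears twice. Null rejection in 10,000 simulated trials per setting:

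| ρ | Rejection at nominal 0.05 |
|---|---|
| 0.3 | 0.030 |
| 0.5 | 0.022 |
| 0.7 | 0.018 |
| 0.9 | 0.018 |

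The test is conservative.

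**3. Participant-adjusted omnibus test** (participant + three-level stimulation). Of the 160 − 1 = 159 df, participants take 79 and stimulation 2, leaving 159 − 79 − 2 = 78 for the residual. Null rejection was 0.048 to 0.053 over the same correlations, and 0.050 when the residual SD of one active condition was 1.5 times larger. The level is correct. Algebraically, this F(2, 78) is a joint test that the mean active-minus-sham change is zero in both arms.

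**4. What an order effect does to that test.** Let both arms shift by o SD from first to second run, with no stimulation effect. The variance of a change is 2(1 − ρ), so the noncentrality is 80·o² / [2(1 − ρ)]. At ρ = 0.7 the denominator is 0.6.

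| o (SD) | Noncentrality | Simulated rejection (5,000 runs) |
|---|---|---|
| 0.1 | 80 × 0.01 / 0.6 = 1.33 | 16% |
| 0.2 | 80 × 0.04 / 0.6 = 5.33 | 51% |
| 0.3 | 80 × 0.09 / 0.6 = 12.0 | 87% |

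Each single contrast with sham is biased by the same amount o.

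**5. Arm x Run.** The estimate is the mean change under excitatory minus the mean change under inhibitory stimulation. A shared shift cancels: (δE + o) − (δI + o) = δE − δI. Simulated rejection with an order effect alone stayed at about 5%.

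**6. Price of Arm x Run.** The SE of one paired contrast is √[2(1 − ρ)/40]; the SE of Arm x Run is √[4(1 − ρ)/40], which is √2 times larger whatever ρ is. At ρ = 0.7 these are 0.122 and 0.173. Suppose an excitatory effect has 80% power as a paired contrast (effect/SE = 2.8) and inhibitory stimulation has no effect. Power for Arm x Run is then 1 − Φ(1.96 − 2.8/√2) = 1 − Φ(−0.02), about 51%.

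**The case against.** The strongest reply is that the ERP sentence is shorthand. The slash list may simply name the conditions, as it does in the description of the switching task, and hypothesis 2 gives the EEG contrasts as each active type against sham. That is a fair reading, and nothing in the plan proposes treating the 160 records as independent groups. It does not settle the matter. The ERP section does not refer to the behavioural models, and importing them would still leave no comparison of change between the randomised arms.

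A reader might infer that the three-condition effect has no valid error term at all. The documents do not support this: the participant-adjusted residual with 78 df gives a test of correct level, and so would a mixed model with a random participant effect. A reader might also infer that the plan commits itself to a specific loss of power. It does not, because it states no ERP model.

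Two further objections stand and shape the fix. Reading stimulation only from Arm x Run would drop the contrasts with sham in hypothesis 2, would cost precision, and would miss a shift common to both active types. And if the mention of two sessions means that each person receives both active types, the factor is fully within-subject and this point falls; the behavioural section's between-subject factor would then be wrong instead.

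**Conclusion.** The point holds as a specification defect with a consequence for interpretation. Under the allocation in the Procedure section, the single ERP stimulation effect cannot be run as an ordinary three-level repeated-measures ANOVA. Run as a between-subject ANOVA it is conservative, at about 0.02 to 0.03 against 0.05. Run with participant adjustment it has the right level but cannot separate stimulation from order; a shared shift of 0.2 SD alone gives rejection in about half of trials.

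These figures assume 40 per arm, alpha 0.05, correlations of 0.3 to 0.9 (0.7 for the order calculation) and illustrative order shifts of 0.1 to 0.3 SD. The documents give none of these, nor any evidence on how large an order effect to expect. Fewer than 40 per arm may have left-sided stimulation, since the behavioural section also lists Hemisphere as a between-subject factor. The structural conclusion depends only on one active type per person and sham first.

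**What to change.** In the Event Related Potentials section, replace the three-condition effect by a mixed model or mixed ANOVA with Arm (excitatory vs inhibitory, between), Run (sham vs active, within) and Language (L1 vs L2, within), with participant as the random unit. Then state:

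- **Randomised comparisons, protected against a shared order effect:** Arm x Run for stimulation, and Arm x Run x Language for the predicted larger effect in L2.
- **Within-arm results:** each active type against sham, and its interaction with Language, as in hypothesis 2, labelled as not protected against order.
- **The limitation:** Arm x Run has √2 times the standard error of a single paired contrast and does not detect a shift common to both active types. This is why the within-arm results are kept.

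In the Procedure section, reconcile the mention of two sessions with allocation to one active type, since the model depends on it.

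The cost is about one paragraph of SAP wording. No added data or testing is needed; the price is the lower precision of the protected comparison.

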Repetitive transcranial magnetic stimulation (rTMS) is increasingly being used as promising therapeutic tool for psychiatric and neurological diseases as well as a valuable tool for neuroscientists investigating underlying mechanisms of cognitive functions (Machii et al., 2005 [10], Lefaucheur et al., 2014 [11]). Neuroimaging, clinical and TMS studies show that the DLPFC plays an important role in processes involving response selection and inhibition (for review see [4]). As such, investigating the effect of rTMS applied to the DLPFC on inhibitory control would allow to further understand the neural substrates and the neural circuitry of inhibitory control.

Aim:

The aim of the present project is to demonstrate the impact of the modulation of the DLPFC on inhibitory control. The experimental task will test the impact of prefrontal stimulation by rTMS (excitatory vs inhibitory) over left and right DLPFC of 80 healthy adult subjects during a simple Go/NoGo task. The hypothesis are that excitatory rTMS of both left and right DLPFC will improve Go/NoGo proficiency, whereas inhibitory rTMS of the right but not left DLPFC will decrease Go/NoGo performance. In total, 80 healthy subjects between 18 and 45 years will be assessed for study B.

Methods:

rTMS

→ see study A

Procedure:

Each participant will take part in two sessions: 1.inhibitory rTMS left DLPFC 2. inhibitory rTMS right DLPFC or 1.excitatory rTMS left DLPFC 2. excitatory rTMS right DLPFC. There will be a two-week interval between the sessions to avoid the crossover of the effects of rTMS. In all sessions, the same evaluations/tasks will be used. The order of left DLPFC stimulation and right

DLPFC stimulation will be counter-balanced.

This study consists of 4 sessions: 1. left excitatory rTMS, 2. Left inhibitory rTMS, 3. Right excitatory rTMS, 4. Right inhibitory rTMS. There will be a two-week interval between each two sessions to avoid the crossover of the effects of rTMS. In all sessions, the same evaluations/tasks will be used. The order the sessions will be counter-balanced.

Participants are seated in an electrically shielded and sound attenuated booth in front of a LCD screen. Stimulus delivery and response recording are controlled using E-Prime 2.0 (Psychology Tools, Inc., Pittsburgh, PA). The stimuli are presented in the center of the screen. Behavioral data will be recorded.

Stimuli and tasks

In the Go/NoGo task, the stimuli are five consonants (S, T, M, H, X) and four vowels (A, E, I, O) presented in black on a white screen. Each trial starts with the presentation of a centered black cross for a duration that randomly varied between 1200 and 2200 ms (100 ms steps). Immediately after the offset of the cross, one of the nine letters is presented in a pseudo-random fashion for 500 ms. Participants have a maximum of 2200 msec to respond. Each subject performs four blocks of 100 trials each.

Participants are instructed to reply as fast as possible by a button press each time a letter is shown on the screen, except for the letter "X". When the letter "X" appears, participants have to withhold their response. To increase response prepotency, the probability of trial occurrence in each block is 0.3 for the no go ("X") and 0.7 for the go. For the Go trials, the probability is equally distributed among the 4 consonants (S, T, M, H) and the four vowels (A, E, I, O)). Each block lasts 3 minutes. Thirty seconds rest periods separate each block. After each rest period, the instructions are shown again to the participant, for a duration of 3 sec.

Behavioral analyses

Performance is indexed by the rate of false alarms (FA, i.e. the proportion of unsuccessfully responded NoGo trials), and RTs to Go stimuli. These indexes are analyzed according to a 2*2 design with the factors Stimulation side (Left; Right) and Stimulation type (excitatory; inhibitory). We expect an interaction between the two factors, driven by an improvement and decrease of performance after right DLPFC excitatory and inhibitory rTMS, respectively, and an improvement of performance after left DLPFC inhibitory rTMS.

References

1. Aron, A.R., *The neural basis of inhibition in cognitive control*. *Neuroscientist*, 2007. 13(3): p. 214-28.
2. Donders, F.C., *On the speed of mental processes*. *Acta Psychol (Amst)*, 1969. 30: p. 412-31.
3. Hirose, S., et al., *Efficiency of go/no-go task performance implemented in the left hemisphere*. *J Neurosci*, 2012. 32(26): p. 9059-65.
4. Chambers, C.D., H. Garavan, and M.A. Bellgrove, *Insights into the neural basis of response inhibition from cognitive and clinical neuroscience*. *Neurosci Biobehav Rev*, 2009. 33(5): p. 631-46.
5. Aron, A.R., T.W. Robbins, and R.A. Poldrack, *Inhibition and the right inferior frontal cortex*. *Trends Cogn Sci*, 2004. 8(4): p. 170-7.

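### Study B counterbalances session order but leaves session out of its 2x2 analysis, so any shift in performance between sessions would go into the error term and cost power

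*Combined protocol and SAP*

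**What the plan says.** Study B, Procedure, describes the sessions in two ways. One paragraph has two sessions per person, with side varying within the person and type between persons: "Each participant will take part in two sessions: 1.inhibitory rTMS left DLPFC 2. inhibitory rTMS right DLPFC or 1.excitatory rTMS left DLPFC", and so on for the right side. In that paragraph, left and right "DLPFC stimulation will be counter-balanced". The next paragraph reads: "This study consists of 4 sessions: 1. left excitatory rTMS, 2. Left inhibitory rTMS, 3. Right excitatory rTMS, 4. Right inhibitory rTMS". It adds: "The order the sessions will be counter-balanced". Both paragraphs state: "In all sessions, the same evaluations/tasks will be used".

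The spacing of sessions is justified only by carry-over of the stimulation: "There will be a two-week interval between the sessions to avoid the crossover of the effects of rTMS". Practice on the task is not mentioned.

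Study B, Behavioral analyses, takes the false-alarm rate and the reaction time to Go stimuli as outcomes. The analysis is given in one sentence: "These indexes are analyzed according to a 2*2 design with the factors Stimulation side (Left; Right) and Stimulation type (excitatory; inhibitory"). The same section expects an interaction of the two factors. No session, period or order term appears anywhere in Study B.

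**The concern.** Each session consists of four blocks of 100 trials, so a participant meets the same speeded task two or four times. A change in speed or accuracy between sessions is plausible, whether from practice or from familiarity with the setting. Counterbalancing spreads such a change evenly over the conditions, which deals with bias. It does not remove the change from the data: one person's left-right difference is pushed up and another's is pushed down, according to the order each received. If the model ignores session, that spread counts as random error.

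The affected tests include the side by type interaction, which carries the hypothesis. The design takes the trouble to balance a nuisance factor, and the analysis as written then does not use it.

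**Working it through.** **Inputs from the documents.** There are 80 participants (Study B, Aim). The factors are side and type. There are two or four sessions per person, order is counterbalanced, and the task is the same each time. No alpha, power, effect size, SD, practice effect or dropout rate accompanies the 80, so that figure cannot be reproduced.

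**Assumptions.** Two-sided alpha is 0.05. The effect is sized to give 80% power with no session shift. For two sessions, 40 participants per stimulation type with order balanced within each type. Session errors are independent once the person's own level is removed.

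**Two sessions.** Let D be left minus right for one person, s the SD of D with no shift, and p the change from session 1 to session 2. D moves by +p in one order and by −p in the other. With equal numbers in each order the mean shift is zero, and ignoring order gives

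Var(D) = s² + p² = s² × [1 + (p/s)²].

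The interaction compares mean D between the two types, 40 v 40. At 80% power, effect divided by standard error is 1.960 + 0.842 = 2.802. Hence

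power = Φ(2.802 / √(1 + (p/s)²) − 1.960).

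| p/s | Variance factor | Power without session | N to hold 80% power (80 × factor) |
|---|---|---|---|
| 0 | 1.00 | 0.80 | 80 |
| 0.25 | 1.06 | 0.776 | 85 |
| 0.3 | 1.09 | 0.765 | about 87 |
| 0.5 | 1.25 | 0.707 | 100 |
| 1.0 | 2.00 | 0.508 | 160 |

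A simulation (20,000 runs per setting, order balanced within type) agrees. At p/s = 0.25, 0.5 and 1.0 the test without session has type I error 0.044, 0.028 and 0.004, and mean bias of about zero. With an order term, power is 0.788 to 0.796 and type I error is about 0.05.

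The side effect has the same variance factor. Its power depends on its own effect size, for which nothing is given. The type effect is not affected here, because each person contributes both sessions to it.

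The ratio must use the SD of the difference. If it were taken against the single-session within-person SD, s₁ (so that s² = 2s₁²), the factor would be 1 + p²/(2s₁²). At ratios of 0.3, 0.5 and 1.0 the efficiency loss would then be 4%, 11% and 33%, instead of 8%, 20% and 50%.

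**Four sessions, both factors within person.** The interaction contrast is (left excitatory − left inhibitory) − (right excitatory − right inhibitory). Its error variance is 4 × SD², where SD is the single-session value. If all 24 orders are used equally, a session profile adds 4 × SS/3, where SS is the profile's sum of squares about its mean.

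- Linear gain g per session (0, g, 2g, 3g): SS = 5g², so 6.67g² is added. The factor is 1 + 1.667(g/SD)². At g/SD = 0.3, 0.5 and 1.0 the factor is 1.15, 1.42 and 2.67, and power is 0.743, 0.653 and 0.403.
- Gain only after session 1 (0, g, g, g): SS = 0.75g², so 1.0g² is added. The factor is 1 + 0.25(g/SD)². At the same ratios power is 0.791, 0.776 and 0.707.

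Because 80/24 is not a whole number, equal use of all 24 orders is an idealisation.

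**Bias.** Suppose 40 completed pairs split 22/18 by order. The mean left-right difference then shifts by (22 − 18)/40 × p = 0.1p. For the interaction, what matters is the difference in this imbalance between the two stimulation types.

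**The case against.** The strongest reply is that the documents show no practice effect. The task is described as simple and the sessions are two weeks apart, so a shift may be negligible. At p/s of 0.25 or less the loss is under 3 points of power. With balanced order the estimates are unbiased and the test errs on the conservative side, so there is no added risk of a false positive. The analysis sentence also gives a factor layout rather than a full model, and it does not forbid an order term. All of this stands as a limit on size and severity.

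It does not remove the point. The factor list is a complete sentence that names two factors, and session is not one of them. The interval is justified by stimulation carry-over, which is a different matter from learning the task. If a shift exists, the term recovers the lost precision. If none exists, the term costs almost nothing.

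A reader might infer three stronger claims that the documents do not support. The first is that practice certainly occurs and the standard errors are known to be too wide; no figure for a shift or an SD is given. The second is that the side and type contrasts are biased; with balanced order they are not. The third is that missed sessions would by themselves bias the contrast. In an analysis of complete pairs, that happens only if the retained orders are unbalanced.

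**Conclusion.** The point holds as a conditional loss of efficiency. If performance shifts between sessions, the stated analysis leaves that shift in the error of the side effect and of the side by type interaction, and also of the type effect if each person has four sessions. For two sessions, interaction power falls from an assumed 80% to about 77%, 71% or 51% at p/s = 0.3, 0.5 or 1.0. For four sessions the loss depends strongly on the shape of the gain: at a shift of 0.5 single-session SD, power is about 65% for a linear gain and about 78% for a gain only after the first session.

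These figures rest on an assumed 80% starting power, balanced orders and, for two sessions, an equal split by type. The Procedure does not say that order is balanced within each stimulation type. If it is not, or if completion upsets the balance, a bias proportional to the shift is added.

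**What to change.** Before the data are seen, pre-specify for both false alarms and reaction time a mixed model with side, type, side by type and session number as fixed factors, and participant as a random effect. Reconcile the two descriptions in the Procedure first, since they decide whether session has two or four levels. State that order is balanced within each stimulation type if type varies between participants.

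The cost is one degree of freedom with two sessions or three with four. No further data, visits or participants are needed. Pre-specification matters because a session term added after results are known could look selective.
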